#### Symptoms of respiratory symptoms

- Go to each household and conduct in-person our baseline survey (same questions as telephone survey). We will elicit consent, as well as collecting demographic information such as age, gender, employment status, and household size information.
- Conduct two waves of follow-up phone surveys to elicit respiratory symptoms and ask about mask use: we will conduct these five weeks after the start of the intervention, and nine weeks after the start, with the potential for longer-term follow-up surveys. We will determine the response rate in the pilot, but our initial estimate is at least 70%.
- Monitor differences in response rates between the treatment and control group to assess whether there is possible response bias from people in the treatment group being more likely to complete our full telephone survey (we suggest other ways of mitigating this potential bias below). For 5,000 randomly chosen households, we will draw blood spots from one adult identified as the highest-risk in their household in terms of number of contacts (2,500 in the control group and 2,500 in the treatment group); the blood spots will be collected in the baseline household survey and used for serology tests. This will allow us to see if survey response rates to our telephone survey correlate differently with baseline infectivity in the treatment and control group.
- Recruit and train local pharmacists to collect data on the number, fraction, and gender of customers that report various symptoms of respiratory infection. Pharmacists will also record the count and purpose of the medicines purchase to treat fever, dry cough or sore throat, and the number of family members with each symptom.

#### Serology tests

- Among adults who report respiratory symptoms in any of our telephone surveys, we will draw blood spots 12 weeks after the initial intervention and conduct serological testing to identify “symptomatic infected”. If the number of symptomatic individuals exceeds 20,000, we will randomly choose 20,000 to be tested in this way from all symptomatic individuals.
- Collect bloodspots for serological testing in 5,000 randomly chosen baseline households. At endline (12 weeks after the intervention begins) we will again collect bloodspots for serological testing in these same 5,000 households.

#### Physical distancing

- Assess if people who are wearing masks are less likely to physically distance themselves from others.

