#### SECTION IV: RESEARCH PLAN

1. **Statement of Purpose:** State the scientific aim(s) of the study, or the hypotheses to be tested.

This study aims to measure the benefits of facemasks in preventing transmission of respiratory infections (especially COVID-19) and to study how different enforcement mechanisms can be used to increase mask use. In particular, this study has six main aims:

1. To develop a scalable intervention that can increase consistent use of a quality mask
2. To assess the impact of appropriately used high-quality masks on the transmission of COVID-19
3. To assess the effect of mask-wearing in reducing the wearer's risk of infection with COVID-19
4. To assess the effectiveness of high-quality cloth vs. "surgical" masks in reducing the spread of COVID-19
5. To evaluate whether increased mask use is associated with risk compensation (an increase in leaving the home or reduced compensation)
6. To assess the protective effect of masks with high filtration and breathability relative to existing face-coverings

We believe that a successful study could influence decision-makers through several channels:

- Our intervention would evaluate whether mask distribution combined with consistent messaging is sufficient to create norms of mask use in places where current mask use is low. Context-appropriate variations of the program we design to increase mask take-up could be replicated in other Asian and African countries with similar implementation and enforcement challenges as Bangladesh.
- Most people in the world still live in countries that do not mandate mask use despite community spread of COVID-19, and mandates may not go far enough. Direct evidence that masks reduce transmission of the virus would strengthen the hand of those pushing for action in those countries.
- Direct evidence of this type would shift the priorities of public health agencies with limited resources if masks are proven effective.
- With direct evidence of the additional protective value of scientifically-validated masks, many individuals, NGOs and governments would invest more in producing such masks.

Additionally, if successful, the intervention in the study will cost-effectively save lives. The above "theory of change" adds to this direct impact.

2. **Background:** Describe the background information that led to the plan for this project. **Provide references** to support the expectation of obtaining useful scientific data.

a) The Case for Mask Adoption

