throughout Bangladesh, compliance was high, with 80-95% of respondents reporting that they wore masks in public areas.

Our more recent data, as well as our conversations with officials, suggests that this trend has now reversed. The Bangladeshi government formally mandated mask use in late May and began fining non-compliers; nonetheless, in our latest survey of mask use, we observed 100,000 people in public areas throughout Bangladesh and found that only 26% were wearing masks despite the severity of the epidemic continuing to increase.

3. **Research Plan:** Summarize the study design and research procedures using non-technical language that can be readily understood by someone outside the discipline. If working with a Non-Government Organization (NGO) or other organization, be sure to highlight which are research-only activities and which activities would occur regardless of the research. If working with survey firms, please specify what research activities the research firm will be responsible for.

We have four main research questions we seek to answer:

1. Can mask distribution and promotion at mosques, markets, and homes successfully change community mask-wearing norms from the status quo to appropriate wearing of high-quality masks?
2. Can community mask-wearing reduce the transmission of symptomatic respiratory infections and symptomatic COVID-19 infection?
3. Does mask-wearing induce risk-compensation such as an increase in leaving the home or reduced physical distancing?
4. Can mask-wearing reduce the risk of COVID-19 infection for the individual mask wearer?

To answer the first three questions, we will randomize an intervention package at the level of markets and associated villages.

To answer the fourth question, we will randomly choose a small fraction of high-risk individuals in control regions and provide them masks and instructions for proper mask use to assess whether masks protect against infection.

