#### Village-level experiment (Research Questions 1, 2 and 3)

#### *Study Design*

We will start by identifying 700 markets, along with the most centrally located village and the mosque attended by most residents of that village. We expect this to comprise about 250 households, or 500 adults per village. We will call this entity a “market+” (plural: markets+).

In order to evaluate whether masks prevent the spread of COVID by preventing transmission and/or protecting the wearer, we will randomize markets+ into treatment and control groups. Our intervention will involve distributing masks at no cost at mosques, markets and directly at people’s homes. We will combine the mask distribution with appropriate behavior change communication and messaging involving imams, market committee leadership and community leaders. We will stratify on markets+ within the same upazila, keeping all markets+ at least 5-10 km apart to minimize spillovers.

Half of the 700 markets+ will be assigned to the treatment group. We intend to stratify to that treatment and control groups are as balanced as possible in terms of ex ante likelihood of COVID-19 infections. To do so, we will: 1) stratify by upazilas and 2) stratify by unions that have similar case rates. For “markets+” that are in the same Upazila and in unions with similar rates of cases, we will list them in order of population and do pairwise stratification by population.

[figure not shown]

Figure 1: Village-level experiment study design

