#### Secondary outcomes:

1. The impact of the intervention on mask use in mosques, markets and other public areas, including the fraction a) appropriately (covering the nose and chin) wearing a mask distributed by our project, b) appropriately wearing a mask that was not distributed by our project, c) inappropriately wearing any a mask or other face covering, or d) are not wearing a face covering at all, and also the fraction specifically wearing our distinctive mask.
2. Prevalence of symptoms of respiratory infection among all individuals for whom we collect phone numbers
3. The prevalence of symptoms of respiratory infection, disaggregated by market vendors, market-goers, imams, mosque-workers, and mosque-goers and none of the above.
4. Number and fraction of pharmacy customers that purchase medicines for symptoms of respiratory infections.
5. Physical distancing behavior measured by direct observation of behavior in mosques.
6. Percentage of adults out of their homes and visiting tea stalls and mosques.
7. Any available data (likely incomplete) on hospitalizations and COVID-19 mortality in each community. This data will be aggregate data which is de-identified from local hospitals and clinics. We expect this data to be sparse and incomplete.
8. Effectiveness of pre-intervention masks by examining the effect size of the intervention with respect to the percent of mask-wearing prior to the intervention. For example, the intervention may increase mask use to 30% in both different treatment villages. If the effect of the intervention on COVID-19 infection rate is the same in villages where people 0% of people were wearing face coverings pre-intervention and where 50% of people were wearing face coverings pre-intervention, this would suggest that the type of face coverings worn prior to the intervention were ineffective.

This analysis uses the variation generated by the randomization but also requires additional assumptions since the baseline rate of mask use is not randomized.

*Intervention activities*

In the treatment arm we will conduct the following intervention activities for four weeks:

- Role modeling
  - Ask imams, public officials and community leaders to commit to wearing masks whenever they leave the house, including while imams deliver prayer at the mosque. It's important to get all influential role-models engaged with our intervention.
- Communities and households:

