### *Data collection*

We will conduct the following activities in both control and treatment arms.

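### The data-collection line on physical distancing compares people by self-chosen mask status, although the causal question on risk compensation is to be answered by randomised arm

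*Protocol*

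**What the plan says.** Section IV.3 (Research Plan) poses question 3 causally: "Does mask-wearing induce risk-compensation such as an increase in leaving the home or reduced physical distancing". It then ties that question to the design: "To answer the first three questions, we will randomize an intervention package at the level of markets and associated villages". Study Design sets the allocation: "Half of the 700 markets+ will be assigned to the treatment group".

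The secondary outcomes of the village-level experiment include, as item 5, "Physical distancing behavior measured by direct observation of behavior in mosques". The item is not conditioned on mask status. Data collection opens with "We will conduct the following activities in both control and treatment arms", and its only entry on distancing is "Assess if people who are wearing masks are less likely to physically distance themselves from others". That entry does not mention the assigned arm.

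Aim 5 in Section IV.1 is worded as an association: "To evaluate whether increased mask use is associated with risk compensation (an increase in leaving the home or reduced compensation".

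Under Intervention activities, worshippers in treatment villages are given a mask as they arrive for Friday prayer. Control groups receive no masks.

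**The concern.** Markets+ are randomised, but mask-wearing by individuals in the village-level experiment is not. Comparing wearers with non-wearers therefore mixes any effect of the mask with the kind of person who wears one. If people who take the epidemic seriously tend both to wear masks and to stand apart, wearers can look more distanced than others even where wearing makes each of them less careful. That would conceal the risk compensation that question 3 is meant to detect.

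The setting adds a second difficulty. Distancing is observed in mosques, and only treatment worshippers are handed masks at the door. Wearers in treatment mosques will include people who would not otherwise have worn one; wearers in control mosques will not. The wearer contrast therefore does not describe the same groups in both arms, and a pooled figure blends two different comparisons.

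At stake is whether the trial's statement on distancing rests on its randomisation or on an observational comparison made inside it.

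**Working it through.** The protocol states no figure for distancing, so there is none to reproduce. The check is a comparison of texts, followed by an illustration. The only document figures in the illustration are the 350 markets+ per arm (half of 700) and 26% mask use, from the Background survey that "found that only 26% were wearing masks". That survey covered public areas nationwide; using it for control markets+ is an assumption. Every other input is assumed.

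**1. The texts side by side.** Question 3 is causal and assigned to the randomised comparison. Secondary outcome 5 names no contrast. Data come from both arms. The one distancing comparison put into words is by mask status. Only aim 5 is worded so that this contrast could serve it.

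**2. Bias of the wearer contrast.** Suppose a share of people are cautious, wear masks more often, and distance more than others by a given gap. Then

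wearer contrast = true effect + gap × D, where D = P(cautious | wearer) − P(cautious | non-wearer).

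Assume a true effect of −5 points, a gap of 20 points and 40% cautious.

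- Control, uptake 50% in cautious and 10% in other people: total use = 0.4×0.50 + 0.6×0.10 = 0.26. D = 0.20/0.26 − 0.20/0.74 = 0.769 − 0.270 = 0.499. Contrast = −5 + 20×0.499 = **+5.0 points**.
- Treatment, uptake 70% and 40%: total use = 0.28 + 0.24 = 0.52. D = 0.28/0.52 − 0.12/0.48 = 0.538 − 0.250 = 0.288. Contrast = −5 + 20×0.288 = **+0.8 points**.
- Pooled over equal arms: D = 0.48/0.78 − 0.32/1.22 = 0.615 − 0.262 = 0.353. Contrast = −5 + 20×0.353 = **+2.1 points**.

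**3. When the sign reverses.** For a true −5 points, this happens once the gap exceeds 5/D points. With the cautious share at 20% to 60%:

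| Mask use | Uptake ratio, cautious to other | D | Gap needed (points) |
|---|---|---|---|
| 26% | 2 to 5 | 0.180 to 0.499 | 10 to 28 |
| 10% to 50% | 2 to 5 | 0.148 to 0.738 | 7 to 34 |
| 26% | 1.5 | 0.098 to 0.135 | 37 to 51 |
| any | 1 | 0 | no bias |

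Combinations that need uptake above 100% are left out.

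**4. The by-arm contrast.** If the package acts on distancing only through masks, its expected value is the true effect × the rise in use, whatever the gap. For a rise of 10 to 40 points this is −5×0.10 to −5×0.40 = −0.5 to −2.0 points. In the example of step 2 it is −5×0.26 = −1.3 points.

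**5. What that contrast could detect.** Assume 30% distancing, 100 people observed per mosque and one mosque per market+. With 80% power and two-sided 5%,

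detectable difference = 2.80 × √[2×0.3×0.7×(ICC + (1−ICC)/100)/350].

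- ICC 0.02: 2.80×√(0.42×0.0298/350) = 1.7 points.
- ICC 0.05: 2.80×√(0.42×0.0595/350) = 2.4 points.
- ICC 0.20: 2.80×√(0.42×0.208/350) = 4.4 points.

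These are before any gain from stratification. Set against 0.5 to 2.0 points, 80% power is reached only near the largest rise in use with the lowest ICC. Divided by a 26-point rise, the detectable effect is about 6 to 17 points per added wearer, above the assumed 5.

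**The case against.** The strongest reply is that the line is a one-sentence data-collection entry and not an analysis specification. The Research Plan already assigns question 3 to the randomised comparison, distancing is an outcome of that experiment, and the entry sits under a lead-in covering both arms. The contrast for a secondary outcome is commonly fixed in a statistical analysis plan, which may exist and is not shown. All of this stands. A reader might infer that the trial will answer question 3 from a non-randomised comparison; the documents do not support that. They support only that the one comparison put into words does not match the stated design.

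The wearer contrast also has a legitimate use, since aim 5 asks about association. That stands too, but the entry does not say that this is its purpose. The bracket in aim 5, which has reduced compensation where question 3 has reduced physical distancing, is a clerical slip and carries no weight here.

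Third, the magnitude is assumed almost throughout, and the gap needed for a reversal runs from 7 to 51 points. The figures show that confounding could matter, not that it will. Reading them as estimates of bias in this trial would go too far.

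Finally, the by-arm contrast is not a clean answer either. It measures the whole package, including messaging from imams and community leaders, and it is diluted. This is correct and limits what the remedy can deliver. It does not rescue the wearer contrast, whose error is of unknown size and does not shrink as more people are observed.

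**Conclusion.** The point holds as a conflict of wording, of minor severity. Taken literally, the entry would give question 3 a confounded answer, and the mosque hand-outs make the wearer group differ between arms. The randomised comparison is implied elsewhere in the protocol and the data for it will be there.

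The size is unknown. With a true −5 points, a 20-point gap and the assumed uptake, the wearer contrast has the wrong sign in both arms (+5.0 and +0.8); with equal uptake in cautious and other people there is no bias. The by-arm contrast keeps the right sign in expectation if the package acts only through masks, but under these assumptions it would often miss an effect of that size. One secondary outcome is concerned. The primary outcome, symptomatic infection, is unaffected.

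**What to change.** Reword the physical-distancing entry under Data collection in two parts.

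- As the answer to question 3: compare distancing of all observed people, regardless of mask status, between treatment and control markets+, with clustering by market+ taken into account.
- As description only: show distancing of wearers and non-wearers separately within each arm, linked to aim 5 and labelled as not randomised.

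Correct the bracket in aim 5 to match question 3 in the same edit.

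The cost is a change of wording, with no new data. The price is a smaller, diluted contrast that reflects the package and not masks alone. The text should say so, and should require a null result to be reported with its confidence interval and not as evidence that there is no risk compensation.

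Separately, the protocol gives two durations for distribution: four weeks under Intervention activities, and throughout the 12 weeks in Section I.1. Those passages must be reconciled, but nothing in this point depends on them.

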### Individual-level experiment (Research Question 4)

### Study design

The goal of the individual experiment is to assess whether mask-wearing reduces the risk of COVID-19 infection for high-risk individuals wearing masks (the “direct effect”, albeit in a different population). We distinguish this from the market+ experiment, where the goal is to assess the joint impact of masks on the spread of the virus via both protection and preventing transmission (the “direct” and “indirect” effects). In order to quantify the potential protective effect of a mask reducing the risk that the mask-wearer becomes infected, we will randomly select high-risk individuals in either control markets+, or in additional markets not included in the original experiment to receive masks. We will specifically randomize within markets, ideally selecting indoor vendors who are physically distant from one another. Because these vendors are such a small fraction of the population within markets+, we do not expect this intervention will appreciably impact mask use in the control group of the larger experiment.

[figure not shown]

Figure 2: Individual-level experiment study design (in green) embedded in Village-level experiment (in blue)

### Intervention activities

- Treatment individuals will be given masks and behavior change communication to motivate proper mask use. They will not be asked to recommend masks to others, but will also not be discouraged from recommending mask use to others.
- Control individuals will receive no masks or behavior change communication

### Outcomes

#### Primary outcome:

1. SARS-CoV-2 infection rates, assessed by comparing baseline to follow-up serology

#### Secondary outcomes:

1. Prevalence of symptoms of respiratory infection
2. Average body temperature
3. The impact of the intervention on mask wearing by market vendors
4. Physical distancing
5. Hospitalizations and mortality of market vendors

### Data collection

We will conduct the following activities among individual-level control and treatment vendors:

## Mask use

- Conduct observations to assess mask use using the same criteria as the above “markets+” experiment

## Symptoms of respiratory infection

- Health worker will conduct interviews with participants in the individual randomization arm to gather data on symptoms of respiratory infection at 0, 5 and 9 weeks, as well as collecting blood spots for serological testing at baseline and at 12 weeks

## Physical distancing

- Conduct observations to assess physical distancing using the same criteria as the above “markets+” experiment

Mask Production, Distribution, and Promotion

Villages in the treatment arm will be randomized to receive cloth masks or surgical masks. The Standard Group, one of the largest manufacturers of ready-made garments in Bangladesh and part of the Bangladesh Garment Manufacturers and Exporters Association (BGMEA) is prepared to produce 400,000+ cloth masks according to our specifications.

After an extensive review of the literature on fabrics for low-cost masks and testing at Stanford University, we have selected to use a mask that has outer layer of 100% non-woven polypropylene, a middle layer of 60% cotton/40% polyester interlocking knit, and an inner layer made of the same interlocking knit, and an inner layer made of the same interlocking knit. The fabric will be sewn into a mask with a flat front panel that bunches near the ears and is affixed to the head with ear straps and a metal wire nose brace. The mask fully covers the nose and mouth even with animated talking. The mask is comfortable, partially because it does not hold hot air over the face. We estimate this mask is approximately 60% efficient at blocking particles 300 nm in size at a flow velocity of 10 cm/s (the particle size and approximate flow velocity specified by the U.S. National Institute of Occupational Safety and Health). This compares to bandanas that are <10% effective at a similar flow velocity and surgical masks which have filtration efficacies ranging from 40-70%.

Surgical masks, made from outer and inner layers of spunbound material and a middle layer of meltblown material, vary in quality but generally have much higher filtration efficiency than cloth masks. Even after surgical masks have been washed 10 times, their filtration efficiency is still higher than most cloth

---

 Producing masks locally in Bangladesh yields an ancillary benefit in that it protects the livelihoods of garment factory workers. The ready-made garment industry is the sector hardest hit by the global COVID-19 shock, with a spate of order cancellations from importers in the US and EU. This disproportionately benefits women and children, as previous research shows that factory jobs allow young women in Bangladesh to delay marriage and childbirth. The BGMEA is itself extremely cognizant of infection risk and is taking numerous measures to reduce employee risk at all facilities, including: maintaining social distancing protocols whenever possible, requiring all employees to wear masks, making available handwashing facilities inside and outside the building, creating an entry plan which allows for each individual to spend 30 seconds washing their hands, and checking temperatures with an infrared thermometer (sending home anyone with a fever) among other procedures (BGMEA Factory Opening Protocol, available on request).

alternatives. We are speaking to surgical mask manufacturers about producing 400,000+ high-efficiency surgical masks to be distributed for this experiment.

The Yale and IPA research teams have substantial experience implementing behavior change programs in rural Bangladesh over the last 12 years, in partnership with many different local implementers. We have marketed improved cookstoves, encouraged seasonal migration, and implemented community-led total sanitation (CLTS) programs to encourage investments in new hygienic latrines. The CLTS program and the latrine construction subsidies we distributed via lottery were much more logically complicated and challenging than mask distribution and monitoring of mask-wearing.

